## 2.0 OBJECTIVES AND SCIENTIFIC AIMS

The primary objectives of this study are:

- To correlate the presence and extent of hypoxia, as defined by F-FMISO FB and BH PET/CT at baseline with 3-year progression-free survival (PFS) and overall survival (OS).
- To assess the predictive value of F-FMISO PET/CT in lung cancer patients undergoing radiotherapy or concurrent chemoradiotherapy, as measured by Breath-Hold (BH) and Free-Breathing (FB) PET/CT images, and to determine whether BH PET/CT provides greater predictive capability than Free-Breathing (FB) PET/CT.

The secondary objective of this study is:

- To assess the predictive value of F-FDG PET/CT in a group of twenty five lung cancer patients undergoing radiotherapy or concurrent chemoradiotherapy, as measured by Breath-Hold (BH) and Free-Breathing (FB) PET/CT images, and to determine whether BH PET/CT provides greater predictive capability than Free-Breathing (FB) PET/CT.

- To assess the feasibility of simultaneous F-FDG and F-FMISO PET dynamic acquisitions in a group of 5 patients undergoing radiotherapy or concurrent chemoradiotherapy. If successful, our approach would allow multi-radiotracer PET exams on the same day reducing the need for extra patient visits. For the patients who will undergo the dual FMISO/FDG study, the mid-treatment FMISO will be optional.

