## **4.0 OVERVIEW OF STUDY DESIGN/INTERVENTION**

### **4.1 Design**

This is a single-institution exploratory study evaluating the prognostic and predictive significance and reproducibility of tumor hypoxia as imaged by F-FMISO PET, in NSCLC patients before receiving any treatments for their disease. In a sub-group of these patients, we will assess the predictive value of F-FDG PET/CT as well. Moreover, in a sub-group of five patients, we will assess the feasibility of simultaneous F-FMISO/F-FDG acquisitions. Patients will be identified in thoracic oncology, radiation oncology, or radiology departments at the time of their planned diagnostic imaging studies.

We will also evaluate the pharmacokinetic properties of F-FMISO during the imaging studies. Moreover, we will evaluate the significance of breath hold (BH) imaging over standard techniques in both F-FDG PET/CT and F-FMISO PET/CT image sets in patients from Group 1, as outlined in Sections 9.1 and 9.2. Patients will be identified and consented prior to their baseline F-FDG-PET/CT. A total of 25 patients will be accrued for this study over a 3 year period; 10 patients who are receiving RT or concurrent chemo RT and 16 patients who are receiving neoadjuvant chemotherapy. The group of 10 patients receiving RT or concurrent chemo-RT will receive an additional repeat F-FDG PET/CT scan at mid-treatment.

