## **12.0 CRITERIA FOR THERAPEUTIC RESPONSE/OUTCOME ASSESSMENT**

There are two primary goals for this study; first, to assess the reproducibility of kinetic analysis of dynamic  $^{18}\text{F}$ -FMISO PET images, in both BH and FB data sets, and second, to assess the prognostic value of hypoxia, as measured with  $^{18}\text{F}$ -FMISO PET, with OS and PFS in NSCLC. As explained above, the presence and extent of tumor hypoxia will be measured by means of kinetic analysis of dynamic  $^{18}\text{F}$ -FMISO PET images. Kinetic analysis parameters may be susceptible to breathing-induced motion artifacts due to patient respiration. Hence, the correlation of outcome to both the presence and extent of tumor hypoxia may be inaccurate. We will therefore conduct analyses based on BH- and FB- PET datasets, and then compare the results in order to assess the effect breathing on these parameters. This exploratory objective of tumor hypoxia correlation to clinical endpoints is dependent on time to tumor progression and death. We will follow up with these patients up to a maximum of three years. The table below summarizes the milestones of this research project.

Likewise, the predictive value of FDG PET may also be suspect due to breathing motion artifacts. In light of the discussion above, therefore, the secondary aim is to compare the predictive value of FDG PET when the data are acquired in BH versus in FB PET.

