## **13.0 CRITERIA FOR REMOVAL FROM STUDY**

If at any time the patient develops unacceptable toxicity he/she will be removed from study. An unacceptable toxicity will be defined by a grade III/IV toxicity requiring hospitalization as per CTCAE v4.0

If at any time the patient is found to be ineligible for the protocol as designated in the section on Criteria for Patient/Subject Eligibility (i.e., a change in diagnosis), the patient will be removed from the study.

Patients who are withdrawn from the study before completing all protocol required scans will be replaced to ensure there are 25 evaluable patients.

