## **14.0 BIOSTATISTICS**

This study will enroll 25 patients with non-small cell lung cancer (NSCLC) who will undergo treatment with definitive conventionally fractionated radiation therapy (RT), neoadjuvant chemotherapy, or chemo-RT. In addition to standard of care PET/CT scans, they will also be scanned twice at baseline (pre-treatment) with experimental  $^{18}\text{F}$ -FMISO scans.

Since some patients will have multiple lesions some of the statistical analyses will be lesion-based and some will be patient-based. This is explained in detail within each analysis but primarily, reproducibility analyses will be lesion-based and analysis of predictive values will be patient-based. Presence and extent of hypoxia will be analyzed twice, one lesion-based and the other patient-based. One of the primary objectives is to evaluate the reproducibility of kinetic analysis in serial, BH and Free-Breathing (FB), dynamic  $^{18}\text{F}$ -FMISO PET images. Hypoxia is measured by  $k_3$ , the trapping rate (see section 7.3). This will be analyzed both as a binary and a continuous variable: if any of the voxels

inside the tumor has a  $k3 > 0.1$  the tumor is defined to be hypoxic while its extent will be defined by the fraction of hypoxic volume which is the fraction of tumor volume with  $k3 > 0.1$ . Reproducibility will be evaluated using Cohen's kappa for presence of hypoxia and concordance correlation coefficient for the extent of hypoxia. This will be a lesion-based analysis and multiple observations per patient will be taken into account using a variance inflation factor estimated from the intraclass correlation coefficient.

Another primary objective is to compare the presence and extent of hypoxia with the clinical outcome (see section 7.3 and above for the definition of hypoxia). Previous studies showed comparable outcomes for stage IIIA (which is the majority treated) when following either of the two treatment arms considered in this study (51, 52).

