Therefore, data from both groups of patients will be analyzed together. Historical data suggests 38% of patients will be free of recurrence at 3 years (53), which provides us with approximately 80% power to detect a hazard ratio of 3.0 between groups of low and high change. This calculation is based on a log-rank test and assumes that extent of hypoxia is dichotomized at observed median resulting in equal group sizes and maximal power. This is for planning purposes only. We will use Cox regression with extent of hypoxia as the covariate in two different ways: (1) lesion-based analysis with an estimating equations to account for multiple observations per patient; (2) patient-based where an aggregate measure of extent of hypoxia (sum of the fraction of tumor volumes with  $k3 > 0.1$  across all lesions) over all lesions within a patient) will be used as a covariate. In addition, a lesion and patient-based analyses for presence of hypoxia will also be considered where, for the patient-based analysis, the aggregate measure will be defined as presence of hypoxia in at least one of the lesions.

In an exploratory analysis to address the secondary objective of assessing the predictive value of FDG PET/CT in a group of twenty five lung cancer patients undergoing radiotherapy or concurrent chemoradiotherapy, we will use the concordance probability estimate from a proportional hazards regression model with SUV as the predictor for the outcomes of survival and progression-free survival. Time of origin will be the start time of therapy (neoadjuvant therapy, if applicable, concurrent chemoradiation or radiation alone otherwise). We will use these estimates to preliminarily determine whether BH PET/CT provides greater predictive capability than Free-Breathing (FB) PET/CT. Since these analyses are exploratory findings will be interpreted as hypothesis-generating.

We expect to accrue one patient a month for each of the two cohorts.

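### Section 14.0 claims about 80% power for a hazard ratio of 3.0 without alpha, sidedness or event count; its own inputs give about 58% (two-sided 5%) or 70% (one-sided 5%)

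*Combined protocol and SAP*

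**What the plan says.** The only power statement in the document is in Section 14.0. It starts from an overall event-free rate, "Historical data suggests 38% of patients will be free of recurrence at 3 years (53"), and continues "which provides us with approximately 80% power to detect a hazard ratio of 3.0 between groups of low and high change". The method follows: "This calculation is based on a log-rank test and assumes that extent of hypoxia is dichotomized at observed median", giving equal groups. The two treatment groups are pooled, and the calculation is described as serving planning only. The analysis to be run is Cox regression with extent of hypoxia as covariate.

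The other inputs are as follows.
- **Sample size.** Section 14.0: "This study will enroll 25 patients with non-small cell lung cancer (NSCLC"). Section 13.0 says patients withdrawn before completing their scans "will be replaced to ensure there are 25 evaluable patients".
- **Follow-up.** Section 12.0: "We will follow up with these patients up to a maximum of three years".
- **Objective.** Section 2.0 relates hypoxia on FMISO "PET/CT at baseline with 3-year progression-free survival (PFS) and overall survival (OS").

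No section gives the significance level, whether the test is one- or two-sided, or the expected number of events.

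**The concern.** Log-rank power depends on the number of events, the hazard ratio, the allocation and alpha. The plan fixes the hazard ratio and allocation, lets the events be derived, and omits alpha. With the derived events, neither usual 5% convention comes near 80%.

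The sentence also describes the compared groups by change, while the objective is hypoxia at baseline and the next sentence splits on extent of hypoxia. No change score is defined for this analysis, so a reader cannot be sure which comparison the power figure describes.

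What is at stake is how the result is read. A null finding would be judged against a stated 20% chance of missing a true hazard ratio of 3.0. On the plan's inputs that chance is about 42% (two-sided 5%) or 30% (one-sided 5%).

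**Working it through.** **Inputs**
- N = 25 (Sections 13.0 and 14.0), with scan withdrawals replaced, so no dropout adjustment.
- 38% of patients recurrence-free at 3 years (14.0) and follow-up of at most three years (12.0), so at most 62% contribute an event.
- Hazard ratio 3.0, log-rank test, 1:1 median split (14.0).
- Alpha and sidedness are not stated. Assumed range: two-sided 5%, one-sided 5%, one-sided 10%.

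**Expected events**

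d = 25 × (1 − 0.38) = 15.5

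**Trying to recover the stated 80%**

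The Schoenfeld formula with equal groups is power = Φ(√d/2 × ln HR − z). Here √15.5/2 × ln 3 = 1.968 × 1.0986 = 2.163. Power of 80% needs z = 2.163 − 0.842 = 1.321, which is a one-sided alpha of about 9.3%. The plan states no such level.

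**Power at the candidate levels**

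| Alpha | z | Schoenfeld power | Simulated log-rank power |
|---|---|---|---|
| two-sided 5% | 1.960 | 58.0% | 56–57% |
| one-sided 5% | 1.645 | 69.8% | 68–69% |
| one-sided 10% | 1.282 | 81.1% | about 80% |

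The simulation used 20,000 runs per setting, 12 against 13 patients, exponential times and censoring at 3 years. The 3-year event-free rates were 57.2% and 18.8%, which average 38% and correspond to a hazard ratio of 3 (0.572³ ≈ 0.188). The Freedman formula is lower at each level: 50.3%, 62.7% and 75.4%.

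**What 80% power would require at a hazard ratio of 3.0**

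d = 4(z + 0.842)² / (ln 3)²
- Two-sided 5%: 26.0 events; 26.0/0.62 gives about 42 patients (44 if events are rounded up to 27).
- One-sided 5%: 20.5 events; 20.5/0.62 gives about 33 patients (34 if events are rounded up to 21).

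**Hazard ratio detectable with 80% power at 15.5 events**

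HR = exp[2(z + 0.842)/√15.5]: 4.15 (two-sided 5%), 3.54 (one-sided 5%), 2.94 (one-sided 10%).

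**Sensitivity to how the inputs are read (Schoenfeld)**

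| Reading | Events | Two-sided 5% | One-sided 5% |
|---|---|---|---|
| N = 26 (the 10 + 16 in Section 4.1) | 16.1 | 59.7% | 71.2% |
| N = 30 (if the 5 Group 2 patients are additional) | 18.6 | 65.9% | 76.5% |
| 38% is the low-hypoxia group's rate, N = 25 | 19.6 | 68.1% | 78.4% |
| 38% is the low-hypoxia group's rate, N = 26 | 20.3 | 69.8% | 79.8% |
| 38% is the high-hypoxia group's rate, N = 25 | 11.2 | 45.1% | 57.7% |
| 20 PFS events assumed | 20 | 69.0% | 79.2% |
| Every one of 25 patients has an event | 25 | 78.4% | 86.5% |

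For the third row, the other group's rate is 0.38³ = 5.5%, so d = 12.5 × (0.62 + 0.945) = 19.6. The last row contradicts the 38% and is shown only as an upper bound for 25 patients.

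**The case against.** The strongest reply is that, with alpha missing, 80% cannot be shown to be wrong. A one-sided 10% level gives 81%. A one-sided 5% level comes close if the 38% is applied to the low-hypoxia group as reference: 78.4% with 25 patients, or 79.8% with the 26 that Section 4.1 implies ("10 patients who are receiving RT or concurrent chemo RT and 16 patients who are receiving neoadjuvant chemotherapy"). The 38% is also freedom from recurrence, while the endpoint is progression-free survival. Deaths without recurrence would normally add events, and an assumed 20 events gives 79.2% at one-sided 5%. Finally, the study is described as exploratory, the calculation is marked as a planning figure, no decision rule depends on it, and the specified analysis is a Cox model rather than a median-split log-rank test.

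Much of this stands. The figure is not impossible, and the consequence is limited. But each route to 80% needs an alpha the plan does not state, and the routes at one-sided 5% also need an input that departs from the text, which applies the 38% to patients overall and gives no PFS event count. At two-sided 5%, 25 patients cannot reach 80% even if all have an event. The exploratory label lowers the stakes but does not supply the missing inputs.

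**Conclusion.** The concern holds. On the plan's literal inputs the power for a hazard ratio of 3.0 is about 58% at two-sided 5% or 70% at one-sided 5%, which is 22 or 10 percentage points below the stated 80%. This rests on 15.5 expected events: 25 patients, 38% recurrence-free overall, complete three-year follow-up, equal groups and the Schoenfeld approximation, which the simulation supports. Earlier censoring would lower the power; a higher PFS event count would raise it. The omission of alpha, sidedness and events is certain. That 80% is a miscalculation is not, since one-sided 10% would reproduce it. The reference to change in the power sentence is a separate wording error. The point should be fixed because this is the only power figure for a primary objective, but it does not affect conduct or the specified analysis.

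**What to change.** Revise the power sentence in Section 14.0 to state alpha, sidedness and expected events, and give the figure that follows. Two forms consistent with the present inputs:
- 25 patients and about 15.5 expected events give about 58% power for a hazard ratio of 3.0 at two-sided 5%, with 80% power at a hazard ratio of about 4.2.
- The same inputs give about 70% power at one-sided 5%, with 80% power at a hazard ratio of about 3.5.

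If one-sided 10% was intended, say so beside the 80%. If the 38% was meant as one group's rate, or more PFS events than 15.5 were expected, state that and its basis. Use one sample size throughout: Section 4.1 gives a total of 25 but components of 10 and 16. Describe the compared groups as low and high baseline extent of hypoxia.

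The cost is one or two sentences, plus the Section 4.1 count. No extra patients and no change to the analysis are needed. Unless one of those other intentions applies, the stated power becomes less favourable.

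### The lesion-based Cox model of PFS and OS repeats one patient outcome per lesion, and its usual robust Wald test can be anti-conservative with only 25 patients

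*Combined protocol and SAP*

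**What the plan says.** Section 14.0 plans two Cox regressions of clinical outcome on extent of hypoxia. The first is a "lesion-based analysis with an estimating equations to account for multiple observations per patient". The second is patient-based and uses the hypoxic volume fractions added up over a patient's lesions. Presence of hypoxia is also analysed at both levels; a patient counts as hypoxic if at least one lesion is. Neither level is named as decisive.

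Earlier in the same section, as a general rule qualified by the word primarily, "reproducibility analyses will be lesion-based and analysis of predictive values will be patient-based". The next sentence says that presence and extent will be analysed at both levels.

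Section 14.0 sets the sample at 25 patients. Section 13.0 adds that patients withdrawn before completing their scans "will be replaced to ensure there are 25 evaluable patients". On follow-up, Section 12.0 says: "We will follow up with these patients up to a maximum of three years". The planning assumption in Section 14.0 is: "Historical data suggests 38% of patients will be free of recurrence at 3 years".

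For the lesion-based Cox model the plan states no variance estimator, type of test, small-sample correction or alpha, and no expected number of lesions per patient. The variance inflation factor based on the intraclass correlation is given for the reproducibility analysis only.

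**The concern.** Progression and death happen to a patient, not to a lesion. A lesion-level Cox model of PFS or OS must therefore copy the same time and status onto every lesion row of that patient. The rows multiply but the outcomes do not, and a patient with more lesions carries more weight.

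Estimating equations are the natural way to allow for this clustering. However, the variance they usually supply is estimated from the spread between patients and tends to be too small when patients are few. Here there are 25 patients and about 15 to 16 events.

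Section 14.0 calls the comparison with outcome a primary objective. With two unranked models, each for extent and for presence, a p-value from the weaker model could be reported as the result.

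**Working it through.** **1. The plan's own figure.** The only operating characteristic given is "approximately 80% power to detect a hazard ratio of 3.0 between groups of low and high change", for a log-rank test with a median split. Expected events: 25 × (1 − 0.38) = 15.5.

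- Schoenfeld: power = Φ(√(d × 0.25) × ln HR − z). Here √(15.5 × 0.25) × ln 3 = 1.969 × 1.0986 = 2.163. Two-sided 5%: Φ(2.163 − 1.960) = 58%. One-sided 5%: Φ(2.163 − 1.645) = 70%. One-sided 10%: Φ(2.163 − 1.282) = 81%.
- Freedman: √15.5 × (3 − 1)/(3 + 1) = 1.969, giving 50%, 63% and 75%.

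The stated 80% is not reached at a 5% level, and the plan states no alpha. That is a separate matter; it is shown here only because it fixes the event count.

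**2. What the lesion rows contribute.** Let patient i have m_i lesions with covariates x_ij, mean x̄_i, and one time t_i and status δ_i. The Cox score (Breslow form) is

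U = Σ_i Σ_j δ_i {x_ij − E(t_i)} = Σ_i δ_i m_i {x̄_i − E(t_i)},

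where E(t) is the lesion-weighted mean in the risk set. Lesions of one patient enter the event term only through their mean, multiplied by m_i. Hence no outcome information is added and weighting is by lesion count. The cluster-robust variance is A⁻¹ (Σ_i U_i²) A⁻¹, where A is the information and U_i is patient i's total score contribution. Its middle term is a sum over only 25 patients.

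**3. Null simulation.** From the documents: 25 patients, 62% events by 3 years, one outcome per patient. Assumed, because not stated: two-sided 5% level; lesions per patient (all one; 80% one and 20% two; 1–3; 1–5; skewed 1–8); within-patient correlation (ICC) of 0, 0.3, 0.6 or 0.9; exponential times. There were 6,000 trials per setting (Monte Carlo standard error about 0.4 points).

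| Analysis, no true effect | Rejection rate |
|---|---|
| Lesion-based extent, cluster-robust Wald, multiple lesions | 6.9–12.3% |
| – at ICC 0 | 6.9–10.0% |
| – at ICC 0.3–0.9 | 8.1–12.3% (mean about 9.6%) |
| – event rate varied from 40% to 85% | 9.2–10.5% |
| Same test, one lesion per patient | 7.8–9.5% |
| Lesion-based, clustering ignored | up to 33% |
| Lesion-based, t(24) reference and G/(G − 1) correction | 5.3–10.0% |
| Lesion-based, robust score test | 4.8–6.6% (7.3% at 85% events) |
| Lesion-based presence, 30–70% of lesions hypoxic (ICC 0.5) | 5.6–7.5% |
| Lesion-based presence, 85% hypoxic (ICC 0.5) | 9.6–11.7% |
| Patient-based sum, model-based Wald | 4.7–6.5% |
| Patient-based sum, each extra lesion multiplying the hazard by exp(0.3) or exp(0.6) | 7.7% or 11.5% |

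A separate simulation of the two models gave 7–8.5% for the lesion-based Wald test and 4.4–5.7% for the patient-based model.

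**4. Size.** 6.9/5 = 1.4 and 12.3/5 = 2.5 times nominal. At no effect, a nominal 95% Wald interval covers in 100 − 12.3 = 87.7% to 100 − 6.9 = 93.1% of trials.

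**5. Cause.** The excess is present with one lesion per patient, where nothing is repeated. With 1–3 lesions and ICC 0.5 it falls from 9.5% at 25 patients to 7.4%, 6.2% and 5.4% at 50, 100 and 200 patients, although lesions are still repeated. The driver is the number of clusters.

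**6. The patient-level sum.** The planned sum equals m_i × x̄_i, so it also acts as a proxy for lesion number. If lesion number is itself prognostic, the sum picks that up, which explains the last row of the table.

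**The case against.** The case for leaving the plan alone has several parts.

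- **Consistency.** A reader might infer that the section contradicts itself by reserving lesion-level work for reproducibility and then using it for outcome. The documents do not support that: the rule is qualified by primarily, and the next sentence announces both levels for presence and extent. What remains is a missing ranking.
- **Cause.** A reader might blame the copied events. The clustered variance largely deals with those; the excess is small-sample bias. The weighting by lesion count is a separate matter of interpretation. That multi-lesion patients dominate the estimate was not computed, and the plan says only that some patients will have several lesions.
- **Method.** The plan says estimating equations. It does not mention a sandwich variance or a Wald test, and a robust score test under the same equations is close to nominal. This stands: the Wald test is the ordinary reading, not a stated choice.
- **Size.** A reader might state as fact that the error doubles. The documents give no lesion counts, correlation or alpha. Across all settings, presence included, the factor runs from about 1.1 (5.6/5) to 2.5.
- **Consequence.** A patient-based model is planned alongside, Section 4.1 calls the study exploratory, and Section 1.0 says the investigational scans will not guide treatment. This lowers the stakes but does not remove the issue. Section 14.0 still calls the outcome comparison a primary objective. Section 12.0 lists it among two primary goals and also calls it exploratory. The hypothesis-generating caveat in Section 14.0 belongs to the FDG analysis.
- **Remedy.** Moving to the patient-based model as written is not automatically safe, because its summed covariate can be inflated too. This stands and shapes the fix.

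**Conclusion.** The point holds in a limited form. The lesion-based model of PFS and OS adds no outcome information and weights patients by lesion count. With 25 patients and about 15.5 expected events, an uncorrected cluster-robust Wald test for extent can raise a two-sided 5% error to about 7–12%, with intervals correspondingly too narrow. The lesion-level presence analysis is close to nominal when 30–70% of lesions are hypoxic and loses that protection near 85%.

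The size rests on assumed lesion counts, within-patient correlation, alpha and choice of test. The direction does not depend on the particular lesion counts or correlations tried: every multiple-lesion setting for extent exceeded nominal. The event rate for OS is not stated, but varying the rate from 40% to 85% changed little. What the documents show is an unspecified small-sample method and no named decisive analysis, not a contradiction and not a demonstrated doubling.

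**What to change.** In Section 14.0:

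1. Name the patient-based Cox model as the decisive analysis of PFS and OS, in line with the section's own general rule, and state alpha and sidedness. Use a model-based variance: a sandwich variance at patient level does not help, and rejected in up to 15.8% of trials in one setting (1–8 lesions, ICC 0.9).
2. Replace the sum of fractions with a patient-level covariate that does not grow with lesion number, such as the volume-weighted or mean hypoxic fraction, or adjust for lesion number. A patient-mean Cox model rejected in 5.2–6.1% of null trials (3,000 per setting); those runs did not make lesion number prognostic. The at-least-one-lesion definition of presence also becomes more likely as lesions increase, so it needs the same care.
3. Present the lesion-based PFS and OS model as descriptive, or test it with a robust score test or a patient-level permutation test. A t(24) correction alone is only a partial repair.

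The cost is SAP wording and slightly wider intervals for the lesion-based result. No extra patients, scans or data are needed.

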The optimal method to quantitate hypoxia using F-FMISO is to perform compartmental analysis of the dynPET images (39-41). This is a method which uses kinetic information from dynamic scans to assess the rate of uptake and entrapment within the hypoxic tumor tissue. However, compartmental analysis is not meaningful on standard clinical PET images of the lung because of respiratory motion during the PET acquisition. Our group at MSKCC has developed a technique for Breath-Hold (BH) PET/CT imaging. During BH PET/CT, patients are asked to hold the breath for as long as possible, and data are acquired only during the time of the BH, using an in-house respiratory tracking device to monitor patient breathing motion (42). PET emission data will be acquired only while the patient is holding the breath as monitored by an external camera and chest sensor. This process will be repeated until a total of 3 min of BH PET data (equivalent to clinical setup) are acquired. We now propose a novel technique to acquire motion-free F-FMISO dynPET images of lung (one 15 cm field of view) to make accurate compartment analysis, and thus quantification of tissue hypoxia, possible. We shall acquire clinical F-FMISO dynPET images in Free-Breathing (FB) with the list mode (LM) option. During the dynamic PET study, the patient's breathing signal will be recorded simultaneously using an in-house developed tracking software assisted by a video camera. The camera is used to monitor the motion of fiducial markers positioned on the patient's abdomen. The patient's breathing signal will be correlated to the PET data on an event-by-event basis and then only those corresponding to end-expiration will be selected for the final PET images, thus resulting in motion-free images. Incorporating all the PET events from the same dynamic PET study results in the FB dynamic PET data set.

In PET/CT, CT images are used to correct for attenuation in the PET images. Spatial matching between PET and CT images is therefore crucial. Therefore, CT images at breathing phases matching those of the PET images will be acquired. PET data will be corrected for attenuation using the phase-matched CT images.

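### Up to 16 hypoxia-outcome analyses serve one primary objective, with no alpha stated and no single lead test named

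*Combined protocol and SAP*

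**What the plan says.** Section 2.0 lists as primary the correlation of baseline hypoxia, from FB and BH images, "with 3-year progression-free survival (PFS) and overall survival (OS"). Section 12.0 lists the prognostic question as one of two primary goals, yet calls the same objective exploratory a few lines later. On image sets it says: "We will therefore conduct analyses based on BH- and FB- PET datasets, and then compare the results".

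Section 14.0 again calls the hypoxia-outcome comparison a primary objective. On the unit of analysis it says: "Presence and extent of hypoxia will be analyzed twice, one lesion-based and the other patient-based". It puts Cox models for extent first, lesion-based and patient-based, and then adds presence: "In addition, a lesion and patient-based analyses for presence of hypoxia will also be considered".

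The one power statement claims "approximately 80% power to detect a hazard ratio of 3.0 between groups of low and high change". It is for a single log-rank test with extent split at the median, and the text says it serves planning only. No significance level, multiplicity rule or single primary test is given for hypoxia. The sentence that commits to a hypothesis-generating reading closes the paragraph on the secondary FDG analysis, not the hypoxia paragraph.

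**The concern.** An objective that is labelled primary and given a power figure will be read as a test. Here the power figure refers to one test, a median-split log-rank, which is not among the planned Cox models. Those models offer many routes to a p-value for the same question.

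If one of them falls below 0.05, the plan gives no basis for saying whether it is the result the study was built to deliver. Section 9.3 adds a freedom not counted in the 16: the k3 cut-off that defines both presence and extent will be re-assessed on the first 12 patients.

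The plan also has its own reason to put one image set first. Section 3.3 says that "compartmental analysis is not meaningful on standard clinical PET images of the lung because of respiratory motion". Section 14.0 does not use that reason to choose between BH and FB for the prognostic claim.

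**Working it through.** **Count.** Section 14.0 gives extent x (lesion, patient) plus presence x (lesion, patient) = 4 Cox models. Section 2.0 gives two endpoints. Sections 2.0 and 12.0 give two image sets. So 4 x 2 x 2 = 16, of which 8 are patient-based. The plan states no such number; it is derived.

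**The plan's power figure.** Inputs from Section 14.0: 25 patients, hazard ratio 3.0, equal groups, and "Historical data suggests 38% of patients will be free of recurrence at 3 years". Expected events are 25 x 0.62 = 15.5. By Schoenfeld's formula, z(power) = sqrt(events/4) x ln(HR) - z(alpha), and sqrt(3.875) x 1.0986 = 2.163.

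- Two-sided 0.05: 2.163 - 1.960 = 0.203, power 58%.
- One-sided 0.05: 2.163 - 1.645 = 0.518, power 70%.
- One-sided 0.10: 2.163 - 1.282 = 0.881, power 81%.

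The stated 80% is therefore met only at one-sided 0.10. At two-sided 0.05 it is approached (78%) only if all 25 patients have an event.

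**False-positive chance with no true effect.** The plan gives no alpha, so each test is taken at an assumed two-sided 0.05. For k independent tests the chance of at least one p < 0.05 is 1 - 0.95^k. That is an upper reference here, because all tests share the same patients. Simulation allows for the overlap:

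| Setting | All 16 tests | 8 patient-based tests |
|---|---|---|
| Independent tests | 56% | 34% |
| Simulation A | 45% | 24-27% |
| Simulation B | 29-38% | 18-22% |

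Both simulations use 25 patients followed for 3 years, with cluster-robust errors for the lesion-based Cox tests.

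- *Simulation A* (1,000 null trials per setting): 13, 6, 4 and 2 patients with 1, 2, 3 and 4 lesions; intraclass correlation 0.4; BH-FB reliability 0.6-0.8; 3-year OS set at 38%. That OS value is an assumption: the plan's 38% is freedom from recurrence, and it gives no 3-year OS.
- *Simulation B* (five scenarios, 1,500 null trials each): 38% progression-free at 3 years; 1-3 lesions per patient; intraclass correlation 0.1-0.4; BH-FB correlation 0.3-0.9; hypoxia prevalence 50-85%.

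Not all of the excess is multiplicity. In design A the lesion-based tests each reject in about 8-9% of null trials, because the cluster-robust variance is too small with 25 clusters; in B they reject in about 5-9%. With every test in design A calibrated to 5% (prevalence assumed 60-80%), the 16-test figure falls to 34-38%, and to 29% at BH-FB reliability 0.95. A multivariate-normal check gives 47% with factor correlations of 0.3-0.5, and 17% with 0.8-0.95.

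**If the plan's leanings are followed.** Patient-based extent on BH images leaves two tests, PFS and OS. The chance lies between 5% (identical tests) and 2 x 0.05 = 10%; simulation puts it at about 8-10%.

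**Would adjustment do instead?** Bonferroni over 16 gives 0.05/16 = 0.0031, critical value 2.955. Then 2.163 - 2.955 = -0.79, or about 21% power for a hazard ratio of 3.0. Naming one test is far cheaper.

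**The case against.** The best defence is that the plan is exploratory and not without order. Section 4.1 calls the whole study exploratory, Section 12.0 says the same of this objective, and Section 3.3 says the imaging will not change management. Section 14.0 states that analysis of predictive value is primarily patient-based, introduces extent before presence, and bases its planning on extent and recurrence. Comparing BH with FB is an objective in its own right, so FB may be there as a comparator and not as a second chance at the prognostic claim.

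Much of this stands. It rules out calling the analyses wholly unranked, and it lowers the stakes. It does not settle the matter: Section 14.0 still says that presence and extent will each be analysed both ways, no text orders PFS against OS or BH against FB for the prognostic claim, and the primary label and power figure remain.

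Two stronger readings are tempting and not supported. A reader might infer that a false-positive finding is likely. A chance above one half needs nearly independent tests. Here BH and FB FMISO images come from the same acquisition, lesion and patient measures coincide in single-lesion patients, and PFS and OS share events. A reader might also infer that the sponsor will claim whichever result looks best. The documents set no success rule for hypoxia, so that would be conjecture.

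**Conclusion.** The concern holds as a gap in specification. Up to 16 analyses address one objective whose status is given both ways, without an alpha or a named lead test. The chance of at least one nominally significant result under no effect is well above 5%: roughly 30-45% for all 16 tests, part of it from anti-conservative lesion-based tests, and about 18-27% for the 8 patient-based tests. It is only about 8-10% if the plan's leanings are followed and BH is taken first.

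The sizes depend on the assumed 0.05 level, lesion counts, correlations and hypoxia prevalence, none of which the documents give. Very strong correlation would bring the 16-test figure down to about 17%. Every setting examined stays above three times the nominal level for all 16 tests, so the direction does not depend on the choice of assumptions. Patient care is not affected; what is at stake is how a positive finding may be read.

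**What to change.** In Section 14.0, name one primary test and its alpha: patient-based Cox regression of PFS on continuous extent of hypoxia from the motion-corrected images. This follows the plan's own leanings and the argument in Section 3.3. State which patients supply those images, since Section 9.2 limits BH scans to Group 1. Label the other analyses supportive or hypothesis-generating, reported as hazard ratios with 95% confidence intervals and no significance claims. Keep BH versus FB as a comparison objective and not as a second test of the prognostic claim. Align Sections 2.0 and 12.0, which list OS and the BH-FB comparison among the primary aims and mix the words primary and exploratory.

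Do not carry the 80% figure over. It belongs to a median-split log-rank test and comes to about 58% at two-sided 0.05 with 15.5 events. Restate power for the named Cox test at its stated alpha.

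The cost is a few sentences in three sections and a new power calculation, with no change to data collection. The real price is that p-values for OS, presence, lesion-based analysis or FB images can no longer carry the headline claim, and that the restated power may look less comfortable.
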